11.1 Analysis Populations

The following analysis sets are defined in accordance with the ICH-E9 guidance:

The Full Analysis Set is based on the intention-to-treat principle and includes all randomized patients. In exceptional cases, patients from the Full Analysis Set may be excluded (will be decided in the database review [DBR] meeting). In such cases, the exclusion will be justified and documented. Patients will contribute to the evaluation “as randomized.”

The Per-Protocol Set includes all patients of the Full Analysis Set who completed the trial without any major protocol violations. Patients in the Per-Protocol Set will contribute to the evaluation “as treated.” This analysis will only be used if it is different than the Full Analysis Set.

The Safety Analysis Set includes all patients receiving at least 1 dose of the IMP. Patients in the Safety Analysis Set will contribute to the evaluation “as treated.”

Analyses of efficacy endpoints will be based on the Full Analysis Set (and the Per-Protocol Set if necessary). This decision will be made in the DBR meeting. The analysis of the safety endpoints will be based on the Safety Analysis Set.

Before data are released for statistical analysis, a blinded review of all data will take place to identify protocol deviations that may potentially affect the results. At this time, it will be determined if patients and/or data should be excluded from the analysis. Furthermore, outliers will be identified by data review according to ICH-E9.

Obviously erroneous data points may be excluded from the analyses or re-analyzed (e.g., serum concentrations). The decision to re-analyze or exclude data points from the statistical analysis is the joint responsibility of the Sponsor, the Principal Investigator, and the Trial Statistician.

Clinical Trial Protocol
ZP4207-16051

Version number: 6.0
Amendment 5.0
Date: 09 September 2016

The patients or observations to be excluded and the reason for their exclusion will be documented and signed by those responsible prior to database release. The documentation will be stored together with the remaining trial documentation. The patients and observations excluded from analysis sets, and the reason for this, will be described in the clinical trial report.

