11.2.2 Analysis of Efficacy

The analysis of BP function endpoints and glycemic endpoints will be on an intention-to-treat basis. In cases where a treatment arm was not completed (and that arm was not repeated according to protocol criteria), available data from that arm will be used in the data analysis.

The Shapiro-Wilk test will be used to determine the normality of the residuals for each comparison. Summary tables that display descriptive statistics, including percentages, means or medians, and standard deviation and/or ranges, as appropriate, will be provided.

A paired t-test or the Wilcoxon signed rank test for comparison of means with normally or non-normally distributed residuals, respectively, will be used. In a secondary analysis, any period effect and any interaction between treatment and period will be looked for, although no such interaction is predicted for the efficacy outcome. Further details will be included in the SAP.

The number of patients and proportions of severe hypoglycemic events, symptomatic hypoglycemia, and carbohydrate interventions due to hypoglycemia with the event counts will be summarized descriptively, and the proportions will be analyzed by a Fisher's exact test if data allow.

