Training on devices [14]		X				
Monitored BP use			X	X		
Plasma glucose sampling [15]			X	X		
ZP4207/glucagon exposure sampling [16]			X	X		
Nausea and infusion site pain VAS and infusion site reaction Draize scale (visit start [17], hourly, & visit end)			X	X		

Clinical Trial Protocol
ZP4207-16051

Version number: 6.0
Amendment 5.0
Date: 09 September 2016

Trial Visit	Visit 1 [1] Screening	Visit 2 Training	Visit 3 [2] [3] [4] [5] (1 st Treatment Visit)	Visit 4 [2] [3] [5] (2 nd Treatment Visit)	Visit 5 ADA Assessment Visit [6]	Visit 6 Follow-Up [7]
Standardized lunch [18]			X	X		
In-clinic exercise [19]			X	X		
Questionnaires (pre & post BP)			X	X		
ADA			X [20]		X	X
Adverse event review			X	X	X	X

1. Once the patient has been enrolled and eligibility has been established, the order of the treatment visits will be randomized in blocks of 2 patients.
2. In Part 1, each patient will participate in 2 treatment visits: 1 with the iPhone-based BP using ZP4207 and 1 with the iPhone-based BP using Lilly glucagon in a randomized order. In Part 2, each patient will participate in 2 treatment visits: 1 with the iLet using ZP4207 and 1 with the iLet using Lilly glucagon in a randomized order. Up to 2 patients may participate in the trial per day.
3. The night before the visit, patients will place a Dexcom G4 CGM sensor in the abdominal skin and calibrate the sensor when prompted using the provided Nova StatStrip Xpress meter. Patients will be asked to arrive at the visit at least 1 hour in advance of the start of the BP having fasted since 12 00 AM the night before (treatment with simple carbohydrate of up to 30 g for a low is allowed). If the patient is not fasted, the visit will be rescheduled within the visit window. If BG is >250 mg/dL, the visit will be rescheduled within the visit window. If BG is <50 mg/dL, treatment with simple carbohydrate is allowed. If the patient experiences persistent hypoglycemia, the visit will be rescheduled within the visit window.
4. Visit 3 will take place at least 48 hours after screening (Visit 1) and no more than 30 days after screening (Visit 1).
5. There will be a 24-hour minimum washout between Visit 3 and Visit 4 and a maximum of 3 weeks between Visit 3 and Visit 4.
6. Visit 5 will take place 10 days ±3 days from Visit 4.
7. Visit 6 will take place 25 days ±4 days from Visit 4.
8. Height and physical examination will be measured at Visit 1 only.

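### The main efficacy comparisons are paired tests without a period term, although visit order is randomised; a period-adjusted main analysis costs one degree of freedom

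*Protocol*

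**What the plan says.** The current protocol text (version 6.0) fixes the following.

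- **Test.** Section 11.2.2: "A paired t-test or the Wilcoxon signed rank test for comparison of means with normally or non-normally distributed residuals, respectively, will be used". A Shapiro-Wilk test on the residuals decides between the two.
- **Period.** The same section: "In a secondary analysis, any period effect and any interaction between treatment and period will be looked for". No interaction is predicted, and further details are left to the SAP.
- **Randomisation.** Appendix A, footnote 1: "the order of the treatment visits will be randomized in blocks of 2 patients".
- **Population.** Section 11.1: "The Full Analysis Set is based on the intention-to-treat principle and includes all randomized patients". Efficacy is analysed on this set. Section 11.2.2 adds: "The analysis of BP function endpoints and glycemic endpoints will be on an intention-to-treat basis".
- **Incomplete arms.** Where an arm was neither completed nor repeated, "available data from that arm will be used in the data analysis".
- **Size.** Section 11 analyses the two Parts separately, and Section 11.2.4 expects 20 to 24 randomised in all. That is about 10 to 12 patients per analysis.

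**The concern.** The design controls visit order, but the main analysis does not use it. This has three possible consequences.

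1. If outcomes differ systematically between the first and second visit, the difference is added in one sequence and subtracted in the other. A paired test counts that spread as random error. With 10 to 12 patients, such a loss of precision matters.
2. If completers are unevenly split between the sequences, part of the period effect remains in the treatment estimate. Blocks of 2 balance allocation, not completion. One withdrawal criterion in Section 10.6.1 is persistent nausea and vomiting thought to be related to glucagon dosing, so loss after Visit 3 could depend on which product came first.
3. A paired test needs a value from both visits. A randomised patient with no data from one visit belongs to the Full Analysis Set but adds nothing to the test.

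**Working it through.** The protocol states that no formal sample size calculation was made, so there is no power figure to reproduce. It gives no SD, effect size, alpha or period effect. **Assumptions:** SD of the within-patient difference = 1; treatment effect τ = 0 or 1 SD; two-sided alpha 0.05; period effect π (visit 1 minus visit 2) of 0 to 1 SD.

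**Model.** Let d be the ZP4207 value minus the glucagon value. Its mean is τ + π when ZP4207 comes first (n1 patients) and τ − π when glucagon comes first (n2 patients). Let n = n1 + n2.

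**Paired test.**
- Its estimate is the mean of all d, so its bias is π(n1 − n2)/(n1 + n2).
- The expected sample variance of d is 1 + 4π²·n1·n2/[n(n − 1)]. At 5:5 this is 1 + 1.11π²: 1.28 for π = 0.5 and 2.11 for π = 1.0.
- It has n − 1 degrees of freedom.

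**Period-adjusted analysis.**
- Its estimate is the average of the two sequence means, in which π cancels.
- Its standard error is √[s²(1/n1 + 1/n2)/4], with s² pooled within sequences and n − 2 degrees of freedom.

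**Balanced sequences, 5:5** (simulation, at least 200,000 replicates per cell):

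| π (SD) | Paired, type I error | Paired, power | Adjusted, type I error | Adjusted, power |
|---|---|---|---|---|
| 0 | 5.1% | 80% | 5.0% | 79% |
| 0.25 | 4.4% | 78% | 5.0% | 79% |
| 0.5 | 3.0% | 72% | 5.0% | 79% |
| 1.0 | 0.7% | 48% | 4.9% | 79% |

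The noncentral t distribution confirms the first row: 0.803 (9 df) against 0.791 (8 df). At 6:6 paired power is 88%, 87%, 82% and 61%, against 88% adjusted.

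**Unbalanced sequences.** Bias of the paired estimate:
- 5:4: π × 1/9 = 0.11π
- 6:4: π × 2/10 = 0.20π
- 5:3: π × 2/8 = 0.25π

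At 6:4 with π = 0.5 SD the bias is 0.10 SD, and its sign depends on which sequence is the larger:
- bias in the direction of the effect: power 81% paired, 77% adjusted;
- bias against the effect: power 63% paired, 77% adjusted.

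The paired test's type I error at 6:4 with π = 0.5 is 3.8%. With no period effect, power at 6:4 is 80% paired and 77% adjusted.

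**The case against.** **Period is not ignored.** A secondary analysis of it is prespecified, so the question is which analysis comes first. That is right, and the point is limited to the main comparison.

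**The period effects are hypothetical.** No passage supports 0.5 or 1.0 SD. The version 5.0 text holds conditions alike between visits: the algorithm is initialised only with weight and the meal and its timing are the same (Section 7.4.1), and the glucose target is locked (Section 6.5). The corresponding version 6.0 sections are not in the part available. At 0.25 SD the two analyses differ by 1 point of power. This stands and limits the size of the gain.

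**False positives are not inflated.** In the balanced settings and at 6:4 the paired test's type I error is at or below about 5%. This stands too. The harm is lost power and, with imbalance, bias.

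**The SAP may settle the details.** It may, but the protocol already names the main test, so that choice is not left open.

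**Conflict with the Full Analysis Set.** A reader might infer that the paired tests contradict the intention-to-treat set. The documents do not support that. A visit stopped early still yields values that can be paired, and Section 11.1 defines who belongs to the set, not how an absent visit is handled. What remains is narrower: a patient with no data from one visit cannot enter the test, and the protocol does not say so.

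**A loss of 17%.** A reader might take 24 randomised less 20 completers as 4 of 24 lost. The figure of 10 per Part is a ceiling in version 5.0 text, not a dropout forecast. A non-completer may also have attended both treatment visits and missed only a later one.

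**Conclusion.** The point holds as an inexpensive improvement to the analysis. The protocol puts an unadjusted paired test first in a crossover whose visit order is randomised. With balanced sequences, which blocks of 2 make the expected case, the paired test is unbiased; it loses about 1 point of power relative to adjustment at a period effect of 0.25 SD, 7 points at 0.5 SD and 31 points at 1.0 SD. With no period effect it is about 1 point better. Bias needs both a period effect and unbalanced completion, and neither is quantified in the documents.

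A reader might quote the fall to 63% power at 6:4 as the cost of not adjusting. That is one direction only; the opposite imbalance favours the paired test. A reader might also conclude that the treatment-by-period interaction test should be removed. In a two-sequence, two-period design it is aliased with sequence and carry-over and compares about 5 patients with 5, so a null result gives little reassurance. But the protocol attaches no decision to it, and it can stay as descriptive.

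The primary endpoint is safety and tolerability, and no efficacy success criterion is stated. These are secondary, exploratory comparisons, and the benefit is modest.

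**What to change.** In Section 11.2.2, and in the SAP, for each Part:

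- **Continuous endpoints:** make the main analysis a linear mixed model with treatment, period and sequence as fixed effects and patient as random, using all available visits. Patients with one visit can then contribute.
- **Skewed endpoints:** compare the within-patient period differences (visit 1 minus visit 2) between the two sequences by a rank-sum test. This still needs both visits, and the text should say so.
- **Paired t-test and signed rank test:** keep as sensitivity analyses, stated to use patients with data from both visits.
- **Treatment-by-period interaction:** label as descriptive.

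The cost is a wording change and one degree of freedom. If there is no period effect, that is about 1 point of power at 5:5 (80% to 79%) and about 3 points at 6:4 (80% to 77%). No change to data collection or sample size is needed.

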11 STATISTICS

For all analysis, the 2 treatment arms from Part 1 (iPhone-based BP) will be compared, and the 2 treatment arms from Part 2 (iLet) will be compared. The analysis of Part 1 will be completely separate from the analysis of Part 2.

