11.2.4 Sample Size Determination

No formal sample size calculations were made. It is expected that between 20 and 24 patients will be randomized in the trial. The sample size is based on a clinical rather than statistical rationale. The sample size is considered adequate to address the primary trial objective of exploring the safety of ZP4207 when used in the BP and with reference to Lilly glucagon used in the BP.

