3.3 Number of Patients

Up to 40 adult patients with T1DM can be enrolled. The upper bound is based on the expectation that some patients will be excluded after the Screening Visit and the possibility that some patients may have to be discontinued before completion (due to, for instance, inter-current illness or patient withdrawal). It is expected that up to 10 patients will complete each part of the trial protocol.

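### Section 11.2.2 tests the hypoglycemia proportions with Fisher's exact test, which ignores that the same 10 to 12 patients supply both arms

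*Protocol*

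**What the plan says.** Protocol Section 11.2.2 (version 6.0) names the outcomes as "The number of patients and proportions of severe hypoglycemic events, symptomatic hypoglycemia, and carbohydrate interventions due to hypoglycemia". They are to be summarized descriptively, "and the proportions will be analyzed by a Fisher's exact test if data allow". The same sentence stands in version 5.0.

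The design puts both treatments in every patient. Appendix A, footnote 2, says "In Part 1, each patient will participate in 2 treatment visits", one with ZP4207 and one with Lilly glucagon, and then "In Part 2, each patient will participate in 2 treatment visits", again one with each. Section 11 fixes the contrast: "the 2 treatment arms from Part 1 (iPhone-based BP) will be compared, and the 2 treatment arms from Part 2 (iLet) will be compared". It adds "The analysis of Part 1 will be completely separate from the analysis of Part 2".

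On numbers, Section 11.2.4 says "It is expected that between 20 and 24 patients will be randomized in the trial", which is about 10 to 12 per part. Section 3.3 of version 5.0 says "It is expected that up to 10 patients will complete each part of the trial protocol"; the matching section of version 6.0 is not in the text available for this review.

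The paragraph of Section 11.2.2 just before the hypoglycemia sentence prescribes a paired t-test or a Wilcoxon signed rank test for comparing means.

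**The concern.** Fisher's exact test compares two independent samples. Here each patient stands in both rows of the table, so the rows are matched. What carries the evidence about treatment is the set of patients whose status differs between the two visits, and in which direction. Fisher's test cannot see this, because it is computed from the two arm totals alone. The section recognizes the pairing for means and drops it for proportions.

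At stake are the p-values for three hypoglycemia event outcomes. The same p-value would be printed for data sets that carry quite different paired evidence, and at this sample size the choice of test can move a result across 0.05.

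**Working it through.** The protocol gives no power, alpha or event-rate figure for these outcomes, so there is no stated result to reproduce. The check compares the planned test with its paired counterpart on the same data.

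**Inputs.** From the protocol: paired design, parts analyzed separately, about 10 to 12 patients per part. Assumed, because the text gives none: two-sided 0.05, complete pairs, event rates of 0.3 or 0.5 under the null, within-patient correlation from -0.4 to 0.7.

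**Fisher.** With x and y patients with an event out of n in each arm, P(X=k) = C(n,k)·C(n,x+y-k)/C(2n,x+y). The p-value sums the probabilities no larger than the one observed.
- 8/10 against 2/10: 2 × (2025 + 100 + 1)/184756 = 0.0230.
- 5/10 against 0/10: 2 × 252/15504 = 0.0325.

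**Exact McNemar.** With b and c patients having an event on one arm only, p = 2 × Σ C(b+c,j)/2^(b+c) for j = 0 to min(b,c), capped at 1. With a patients having events on both arms, b = x - a and c = y - a.

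| Arm totals, n=10 | Both arms (a) | Split b:c | Fisher | Exact McNemar |
|---|---|---|---|---|
| 8 vs 2 | 2 | 6:0 | 0.023 | 2/64 = 0.031 |
| 8 vs 2 | 1 | 7:1 | 0.023 | 2 × (1+8)/256 = 0.070 |
| 8 vs 2 | 0 | 8:2 | 0.023 | 2 × (1+10+45)/1024 = 0.109 |
| 5 vs 0 | 0 | 5:0 | 0.033 | 2/32 = 0.0625 |

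**All possible tables.** There are C(n+3,3) complete paired tables: 286 at n=10 and 455 at n=12. Running both tests on each one gives 12 tables (n=10) and 26 tables (n=12) where Fisher is at or below 0.05 and exact McNemar is not. There are none the other way round. The size of the p-value is not one-directional, however: at n=12, 9/12 against 3/12 with a 6:0 split gives Fisher 0.039 and McNemar 0.031.

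**Actual size of Fisher's test at nominal 0.05**, by full enumeration of the paired multinomial:

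| n, event rate | corr. -0.4 | 0 | 0.3 | 0.5 | 0.7 |
|---|---|---|---|---|---|
| 10, 0.5 | 0.0351 | 0.0128 | 0.0034 | 0.0008 | 0.0001 |
| 10, 0.3 | 0.0328 | 0.0119 | 0.0031 | 0.0007 | 0.0001 |
| 12, 0.5 | 0.0556 | 0.0228 | 0.0068 | 0.0017 | 0.0002 |

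The size varies with the correlation that the test ignores, and also with event rate and n. For comparison, exact McNemar at n=10 and rate 0.5 has size 0.0176, 0.0090 and 0.0006 at correlations -0.4, 0 and 0.5.

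**Power, Fisher against exact McNemar.** For 70% against 20%: n=10, 42.6% against 35.8% (correlation 0) and 40.2% against 37.7% (0.3); n=12, 61.0% against 50.2% (0) and 61.8% against 60.3% (0.3).

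**The case against.** The best defense is practical. These are secondary endpoints; the primary endpoint is safety and tolerability. No sample size was calculated, the descriptive summary comes first, the test runs only where the data permit it, and no decision in the text shown hangs on these p-values. Positive correlation is what one expects within a patient, and there Fisher's size is far below nominal. At this n Fisher also has somewhat more power than exact McNemar in the cases run. All of that stands, and it limits the severity.

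It can also be said that Section 11.2.2 is only an outline and that the SAP could apply Fisher's test to discordant patients by sequence, the Mainland-Gart form, which is valid in a crossover. The protocol does not say this. It names the test and applies it to the proportions, so an SAP that follows the wording inherits the problem. The proviso about the data concerns feasibility and does not restore the pairing.

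Three stronger readings are tempting and are not supported:
- A reader might infer that false positives are inflated. In the range examined the size exceeded 0.05 only at n=12, rate 0.5 and correlation -0.4, and a negative correlation is not what one expects here.
- A reader might infer that a paired test would recover power, perhaps by picturing both parts together. Section 11 keeps the parts separate, and at 10 to 12 patients the computed power goes the other way.
- A reader might infer that hypoglycemia gets no paired comparison at all. The paired tests for means in the same section already cover carbohydrate grams, and plausibly the event counts.

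**Conclusion.** The point holds. The planned test assumes independent groups where the design supplies matched ones, and it conflicts with the paired tests in its own section. The defect is a p-value with the wrong reference distribution: it does not respond to how many patients changed status, and its error rate depends on a correlation that the test ignores. In practical terms, at 10 and at 12 patients it calls some results significant that the exact paired test would not, such as 5/10 against 0/10 (0.033 against 0.0625), and never the reverse. Under the expected positive correlation it remains conservative overall.

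The p-value comparisons assume two-sided 0.05 and complete pairs; the size and power figures also rest on assumed event rates and correlations. This should be fixed, but it is not critical, because the endpoints are secondary and unsized.

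**What to change.** In Section 11.2.2, and in the synopsis and SAP where they repeat the sentence, replace Fisher's exact test with an exact McNemar test, run separately in each part, on each patient's indicator of at least one event per visit. If period is to be allowed for, use the Mainland-Gart or Prescott test instead. Show the paired 2x2 table and the paired risk difference with a 95% CI. Descriptive reporting of the paired table without a test would also be acceptable.

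The cost is one sentence and no new data. There are two downsides to accept. Power was lower than Fisher's in every case above, by 1.5 points (61.8% against 60.3%) to 10.8 points (61.0% against 50.2%). And p<0.05 needs at least 6 discordant patients, all in one direction if there are exactly 6, since 5:0 gives 0.0625 and 6:0 gives 0.031. Patients with data from one visit only drop out of the paired test and should be shown in the descriptive summary.

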11.2.3 Interim Analysis

An interim database lock may occur upon completion of Part 1 of the trial to analyze the iPhone-based BP data.

11.2.4 Sample Size Determination

No formal sample size calculations were made. It is expected that between 20 and 24 patients will be randomized in the trial. The sample size is based on a clinical rather than statistical rationale. The sample size is considered adequate to address the primary trial objective of exploring the safety of ZP4207 when used in the BP and with reference to Lilly glucagon used in the BP.

